### 10.1. Adverse Events

Adverse events (AEs) will be recorded from the signing informed consent through end of study. AEs will also be assessed for severity, relationship to study drug, and seriousness. AEs will be considered treatment-emergent if their onset occurs following the date of first dose up to the study completion date. Each TEAE will also be categorized according to the treatment period in which it occurs, in order to attribute and summarize an AE based on treatment received at time of event (i.e., during placebo or active treatment). Events that occur during the washout period between Treatment Period 1 and 2 will be attributed to the treatment received in Period 1, and events occurring after Treatment Period 2 up to the End of Study visit will be attributed to the treatment received in Period 2.

Any missing severity assessments will be assumed to be severe, missing relationship assessments will be assumed to be related, and missing seriousness assessments will be assumed as serious.

An overview of AEs will be produced, including counts and percentages of subjects with any incidences of: treatment-emergent AEs (TEAEs), serious AEs (SAEs), related AEs, unrelated AEs, AEs by maximum severity, AEs leading to treatment withdrawal and AEs leading to death.

Sponsor: CuraSen Therapeutics, Inc.  
Protocol Number: CST103/CST107-CLIN-011  
Version and Date: [REDACTED] v1.0 / 24May2022

Adverse events will be coded based on the Medical Dictionary for Regulatory Affairs (MedDRA 23.1) for reporting by system organ class (SOC) and preferred term (PT) in descending order of overall incidence.

Summaries of adverse events by SOC and PT will include the following types:

- TEAEs;
- SAEs; and
- Related AEs.

A summary of TEAEs by SOC, PT, and maximum severity will also be prepared.

A comprehensive listing of all AEs will be provided in a by-subject data listing. In addition, the following listings will be provided:

- SAEs;
- Related AEs; and
- AEs leading to study drug termination

## 10.2. Clinical Laboratory Evaluations

Hematology and clinical chemistry will be reported based on the International System of Units (SI). The following laboratory evaluations will be summarized using descriptive statistics:

- **Hematology:** hematocrit, hemoglobin, mean corpuscular hemoglobin (MCH), mean corpuscular hemoglobin concentration (MCHC), mean corpuscular volume (MCV), platelet count, red blood cell (RBC) count, white blood cell (WBC) count with differential, and reticulocyte count.
- **Clinical chemistry:** albumin, alkaline phosphatase (ALP), alanine aminotransferase (ALT), aspartate aminotransferase (AST), BUN, calcium, bicarbonate, serum creatinine, creatinine phosphokinase (CPK), glucose, lipase, phosphate, potassium, sodium, total bilirubin, total cholesterol, total protein, triglycerides, and uric acid. Additionally, the following chemistry parameters collected at Screening only will be included in these outputs: thyroid-stimulating hormone (TSH) and calculated creatinine clearance according to the Cockcroft-Gault equation.

Observed values and changes from screening/baseline, when applicable, for the above laboratory evaluations will be summarized at each visit.

This data will also be summarized in shift tables of baseline to each visit based on range categories of low (below lower limit of normal [LLN]), normal, and high [above upper limit of normal [ULN]].

All laboratory results will be provided in subject data listings. The following additional results will be included in these listings:

Sponsor: CuraSen Therapeutics, Inc.  
Protocol Number: CST103/CST107-CLIN-011  
Version and Date: [REDACTED] v1.0 / 24May2022

- **Urinalysis and microscopy:** appearance, occult blood, glucose, leukocyte esterase, nitrite, pH, protein, urobilinogen by dipstick, a reflex microscopic urinalysis will be performed if dipstick protein, nitrite, leukocyte esterase, or occult blood results are positive.
- **Serology:** HIV Ab, HbsAg, HbsAb, and HCV Ab (Screening only).
- **Immunology:** SARS-CoV-2 (Screening only).
- **Pregnancy and FSH Tests:** Both urine and serum pregnancy tests will be presented.
- **Urine Drug and Alcohol tests:** Drug tests will include amphetamine, barbiturates, cocaine, opiates.

Box plots of observed results or change from baseline at each visit for potassium and glucose results for each treatment group may be generated.

### 10.3. Vital Signs

Vital signs will include the following: systolic and diastolic blood pressure (mmHg); heart rate (beats/min), temperature (°C), and respiratory rate (breaths/min). Any vital signs taken in triplicate will be averaged within timepoint.

Observed values and changes from screening/baseline for vital signs will be summarized at each visit and time point. For parameters collected as triplicate measurements, the average of the non-missing measurements will be summarized.

Summaries will be presented by treatment at the time of data collected (i.e., Placebo and CST-103/CST-107).

All vital sign data will be listed.

Box plots of observed results or change from baseline at each visit for heart rate results for each treatment group may be generated.

### 10.4. Electrocardiogram (ECG)

ECG parameters include: Heart rate, PR interval, RR interval, QRS interval, QT interval and QTcF. Observed values and changes from baseline for ECG parameters will be summarized at each visit and time point.

Electrocardiograms (ECGs) will be interpreted using the following categories: Normal; Abnormal Not Clinically Significant; and Abnormal, Clinically Significant.

Clinical interpretation will also be summarized at each visit and time point.

Additionally, the number and percentage of subjects in each of the following QTcF categories will be tabulated by visit and timepoint:

- $QTcF \leq 450$  msec
- $450 \text{ msec} < QTcF \leq 480$  msec

Sponsor: CuraSen Therapeutics, Inc.  
Protocol Number: CST103/CST107-CLIN-011  
Version and Date: ██████ v1.0 / 24May2022

- $480 \text{ msec} < \text{QTcF} \leq 500 \text{ msec}$
- $\text{QTcF} > 500 \text{ msec}$
- $\text{QTcF}$  change from baseline of  $\leq 30 \text{ msec}$
- $\text{QTcF}$  change from baseline of  $> 30 \text{ msec}$  and  $\leq 60 \text{ msec}$
- $\text{QTcF}$  change from baseline of  $> 60 \text{ msec}$

Box plots of observed results or change from baseline at each visit and timepoint for QTcF results for each treatment group may be generated.

## 10.5. Physical Examinations

Physical examinations will be presented in subject data listings. The following body systems will be assessed:

- General appearance
- Head, Neck, Thyroid
- Ears, Eyes, Nose, Throat, Mouth
- Chest (excluding breasts)
- Respiratory
- Cardiovascular
- Lymph nodes
- Abdomen
- Skin, Hair, Nails
- Musculoskeletal
- Neurological
- Other

## 10.6. Columbia-Suicide Severity Rating Scale (C-SSRS)

The Columbia-Suicide Severity Rating Scale measures four elements: the severity of ideation, the intensity of ideation, behavior and lethality. The C-SSRS consists of 10 categories, with a binary response option (yes/no). Categories include:

1. Wish to be Dead
2. Non-specific Active Suicidal Thoughts
3. Active Suicidal Ideation with Any Methods (Not Plan) without Intent to Act
4. Active Suicidal Ideation with Some Intent to Act, without Specific Plan
5. Active Suicidal Ideation with Specific Plan and Intent
6. Preparatory Acts or Behavior
7. Aborted Attempt
8. Interrupted Attempt
9. Actual Attempt (nonfatal)
10. Completed Suicide.

Sponsor: CuraSen Therapeutics, Inc.  
Protocol Number: CST103/CST107-CLIN-011  
Version and Date: [REDACTED] v1.0 / 24May2022

The C-SSRS will be completed at Day 1 (Baseline), Day 7, Day 14, and Follow-Up. The outcome of the C-SSRS is a numerical score obtained from the 10 categories stated above.

In addition, three C-SSRS composite indicator variables will be calculated as follows:

*(1) C-SSRS suicidal ideation indicator*

A composite indicator of C-SSRS suicidal ideation (Items 1-5 above) will be calculated as:

- IF the response to any one of the five suicidal ideation questions is “Yes”, THEN set the suicidal ideation indicator equal to 1.
- OTHERWISE, set the suicidal ideation indicator equal to 0.

*(2) C-SSRS suicidal behavior indicator*

A composite indicator of C-SSRS behavior ideation (Items 6-10 above) will be calculated as:

- IF the response to any one of the five suicidal behavior questions is “Yes”, THEN set the suicidal behavior indicator equal to 1.
- OTHERWISE, set the suicidal behavior indicator equal to 0.

*(3) C-SSRS suicidal ideation or behavior indicator*

A composite indicator of C-SSRS suicidal ideation or behavior will be calculated as:

- IF the response to any one of the 5 suicidal ideation questions or any of the 5 suicidal behavior questions is “Yes”, THEN set the suicidal ideation or behavior indicator equal to 1.
- OTHERWISE, set the suicidal ideation or behavior indicator equal to 0.

The C-SSRS will be evaluated in the Safety Set based on methods described by Nilsson. The number and percentage of subjects with any suicidal ideation and/or suicidal behavior following the first dose of study drug will be tabulated.

For the composite endpoint of suicidal ideation, the number and percent of subjects who experience any one of the five suicidal ideation events at least once during treatment through follow-up will be tabulated.

For the composite endpoint of suicidal behavior, the number and percent of subjects who experience any one of the five suicidal behavior events at least once during treatment through follow-up will be tabulated.

For the composite endpoint of suicidal ideation or behavior, the number and percent of subjects who experience any one of the ten suicidal ideation or behavior events at least once during treatment through follow-up will be tabulated.

Results from the C-SSRS will be presented in a listing.

Sponsor: CuraSen Therapeutics, Inc.  
Protocol Number: CST103/CST107-CLIN-011  
Version and Date: [REDACTED] v1.0 / 24May2022

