### 6.4. Missing Data and Data Imputation Rules

All attempts will be made by the Data Management team to ensure completeness of data. Generally, missing data will not be imputed, and will be presented as collected in the study database.

In cases where adverse event (AE) or medication dates are missing, the imputation methods described in Appendix 1 will be used to determine flags for treatment-emergent events, and concomitant medications.

Other missing data methods will be proposed within the respective analysis section, as needed.

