## 7. STUDY SUBJECT DATA

### 7.1. Analysis Populations

**Intent to Treat Set (ITT):** All subjects who have signed informed consent and have been randomized to a treatment sequence. Subjects will be analyzed according to the treatment sequence assigned at randomization. The ITT will be the analysis set for disposition and select baseline characteristic analyses.

Sponsor: CuraSen Therapeutics, Inc.  
Protocol Number: CST103/CST107-CLIN-011  
Version and Date: [REDACTED] v1.0 / 24May2022

**Safety Set (SAF):** All subjects who received at least 1 dose of study drug (CST-103/CST-107 or placebo). Subjects will be reported based on the treatment and dose received. The Safety Set will be used for the reporting of safety analyses.

**Full Analysis Set (FAS):** All randomized subjects who have taken at least 1 dose of blinded study drug (CST-103/CST-107 or Placebo). Subjects will be analyzed according to the treatment assigned at randomization. The Full Analysis Set will be used for evaluating the pharmacodynamic endpoints, and selected secondary endpoints.

**Per-Protocol Set (PPS):** A subset of the Full Analysis Set who sufficiently complied with the protocol. The analysis set will only include subjects without protocol deviations classified as “major”. The Per Protocol Set may be used for selected safety analyses.

**BioStamp Set (BSS):** A subset of the Full Analysis Set who have at least one BioStamp measurement during the baseline period each of the post-baseline periods. The BioStamp Set will be used for demographics and the BioStamp related endpoints.

**Pharmacokinetic Set (PKS):** All subjects in the Safety Set who have at least one valid plasma concentration assessment for CST-103 or CST-107. Subjects will be analyzed according to the treatment received. The PKS will be the analysis set for PK concentration and PK parameter analyses.

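### SAP 10.6 codes an undone or unanswered C-SSRS as no suicidal ideation or behavior, against the SAP's own conventions for missing data (minor)

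*SAP*

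**What the plan says.** SAP 10.6 lists five ideation and five behavior categories with yes/no responses and builds three indicators from them. For ideation, any Yes among the first five leads to "THEN set the suicidal ideation indicator equal to 1", and everything else to "OTHERWISE, set the suicidal ideation indicator equal to 0". The other two have the same second branch: "OTHERWISE, set the suicidal behavior indicator equal to 0" and "OTHERWISE, set the suicidal ideation or behavior indicator equal to 0". No branch gives a missing value, and none requires that the form was completed.

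The section then states that "The C-SSRS will be evaluated in the Safety Set". It tabulates the number and percent of subjects with at least one event from treatment through follow-up. SAP 7.1 puts a subject in the Safety Set after a single dose, with no requirement for a post-dose C-SSRS. SAP 10 presents safety summaries other than laboratory data by cohort, disease type and treatment taken.

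Two general rules bear on this:

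- SAP 5 bases categorical percentages on non-missing values, unless stated otherwise, and displays missing values as their own category.
- SAP 6.4 says that, generally, "missing data will not be imputed, and will be presented as collected in the study database". It leaves other methods to the individual analysis sections. SAP 10.6 names no missing-data method.

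**The concern.** The second branch answers a question that was never put to the subject. Read literally, a blank form becomes a negative finding, and it does so without being described as imputation. Once every subject has a 0 or a 1, the SAP 5 safeguards (non-missing denominator, separate missing category) have nothing left to work on, and a reader of the table cannot see how many subjects were actually assessed.

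The outcome is one that the plan singles out. Protocol 1.3 names suicidal ideation as a standing concern with CNS-active drugs and says that subjects will be monitored for it, and the objectives describe both Cohort A populations as having depressive symptoms. A percentage that can move only downward when data are missing is an unwelcome property there. If more assessments are missed on one treatment than on the other, that treatment's percentage is lowered more.

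**Working it through.** **The rule applied to item sets.** Take the five ideation items and code 1 if any is Yes, otherwise 0:

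| Responses | Indicator under SAP 10.6 |
|---|---|
| five No | 0 |
| four No, one missing | 0 |
| five missing | 0 |

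The three situations cannot be told apart after derivation.

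**Effect on the percentage.** The documents state no C-SSRS rate and no rate of missed assessments, so there is no figure to reproduce. Let N be the subjects in the Safety Set, k the subjects with at least one Yes, and m the subjects with no Yes and no usable assessment.

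- As written: k/N.
- Among assessed subjects: k/(N − m).
- Difference: k·m / [N(N − m)], which is zero if k = 0 or m = 0 and positive otherwise.

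N = 40 is the planned size in SAP 4.3. The values of k and m are assumptions.

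| k | m | As written | Among assessed |
|---|---|---|---|
| 0 | 2 to 8 | 0/40 = 0% | 0/38 to 0/32 = 0% |
| 1 | 2 | 1/40 = 2.5% | 1/38 = 2.6% |
| 1 | 4 | 1/40 = 2.5% | 1/36 = 2.8% |
| 1 | 8 | 1/40 = 2.5% | 1/32 = 3.1% |

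For k = 1 and m = 8 the difference is 8/(40 × 32) = 0.6 percentage points. In relative terms the reported rate is (N − m)/N of the rate among the assessed, here 32/40 = 0.80.

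**With no cases.** The percentage is 0% either way, but the amount of evidence differs. The exact one-sided 95% upper limit for 0/n is 1 − 0.05^(1/n): 7.2% for n = 40 and 8.9% for n = 32. The SAP plans no such limit; the figures only show why the number assessed should be visible.

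**How many subjects could be unassessed.** The Schedule of Events, with its note that the C-SSRS is skipped on Day 1 of Period 1, leaves six administrations after the first dose: Days 7 and 14 of Period 1, Days 1, 7 and 14 of Period 2, and Follow-Up. In a table over the whole study a subject must miss all six to be wholly unassessed. In a by-treatment table there are fewer to miss. Protocol 4.5 and 4.5.2 also ask early withdrawals to attend a withdrawal visit and a Follow-Up Visit, and the C-SSRS is scheduled at both. Withdrawal of consent and loss to follow-up are listed withdrawal reasons, however, and either can leave a dosed subject with no data. A small m is therefore more plausible than a large one.

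**The case against.** The best defense is that the rule was never meant for absent forms. It speaks of the response to a question, so it can be read as applying only to completed assessments, with SAP 5 then supplying a non-missing denominator. A zero default may also be there to cover items that the form allows to be left blank. SAP 10.6 further cites an external scoring guide that may settle denominators and missing data.

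Part of this stands. A programmer who derives the indicator only where a completed record exists would largely avoid the problem, and a correction must not turn legitimately skipped items into missing values. But the SAP does not limit the rule to completed forms, a form returned with blanks falls in the second branch on its plain wording, and nothing in the SAP lets the cited guide override the explicit algorithm. The guide cannot be checked from these documents.

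It is also fair to say that nothing recorded disappears. Every Yes enters the numerator, C-SSRS results are listed by subject, and SAP 7.2 lists reasons for visits not done. Protocol 8.10 planned only a listing, so the tables are an addition. The listing does not, however, correct the tabulated percentages.

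A reader might infer that the rule is the reverse of the adverse-event convention in SAP 10.1, where "Any missing severity assessments will be assumed to be severe" and missing relationship and seriousness are also taken at their worst. The documents do not support that reading. The adverse-event rule fills in attributes of an event that was already reported; it never presumes that an unreported event occurred. The two rules concern different things.

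**Conclusion.** The point holds as a minor defect. SAP 10.6 states a rule that, taken literally, gives a wrong value for undone or unanswered assessments and keeps those subjects in the denominator, contrary to SAP 5 and SAP 6.4. The reported percentage can be lowered or left unchanged, never raised. With N = 40 and the assumed one case and 2 to 8 unassessed subjects, it reads 2.5% instead of 2.6% to 3.1%; with no cases there is no difference.

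These sizes rest on assumed k and m, and the comparison rate describes assessed subjects only; it says nothing about those not assessed. Two further inferences would go too far. The documents do not show that suicidality would be concealed or that monitoring is weakened: monitoring is by rater interview at visits and does not depend on this table. Nor do they show which treatment would look better, since they give no information on missed assessments by treatment.

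**What to change.** In SAP 10.6, define each of the three indicators as:

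- 1 if any relevant item is Yes;
- 0 only if the assessment was done and the items applicable on the form were answered with no Yes;
- missing otherwise.

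For the tables, use as denominator the subjects with at least one post-dose C-SSRS on the treatment concerned, and show the number not assessed by treatment. State to which treatment the Period 2 Day 1 and Follow-Up assessments count, since the SAP gives such an attribution rule for adverse events but not for the C-SSRS. Coding missing responses as Yes is not needed.

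The cost is a few lines of SAP text and the matching programming. No new data and no protocol change are required.

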Study Procedures	
After informed consent, all subjects will complete screening procedures and tests to establish eligibility, which will be performed between Day -28 and Day -8. Subjects who meet eligibility criteria based on screening assessments may be enrolled in the study.
 
Screening procedures include medical history evaluation, body weight and height measurements, physical exam, vital signs (including blood pressure, heart rate, respirations, temperature), ECGs, Columbia-Suicide Severity Rating Scale (C-SSRS), safety laboratory tests (chemistry, hematology, and urinalysis), creatinine clearance calculation, drug and alcohol tests, SARS-CoV-2 status assessment, serum HIV, and Hepatitis B and C screen. A serum β-hCG pregnancy test must be completed for women of childbearing potential. Postmenopausal women will need to complete a follicle-stimulating hormone (FSH) test.
 
Subjects with a positive drug screen (including alcohol) at Screening will be rechecked and if positive will be excluded from participation in the study.
 
During the Screening Visit, the following disease and cognitive assessments and measures will be completed as required to evaluate eligibility for each population: DCFS, MHYS, MoCA, RBD1Q, and DSST.
 
Once all screening visit procedures are completed and the subject meets all eligibility criteria, the subject will return to the site to begin the Lead-In Period (up to 14 days). At that time, the subject will be randomly assigned to treatment. During the Lead-In Period, the subject will be trained on and practice the CANTAB tests and verbal fluency test (alphabet & category), and complete the ESS. The Lead-In Period will also be used to establish a baseline activity profile using a digital device. The BioStamp digital device will be dispensed to the subject who will be instructed to wear it for 7 consecutive days prior to the Treatment Period 1 – Day 1 Visit.
 
At the conclusion of the Lead-In Period, subjects will return to the clinic to begin the treatment periods. During each treatment period, subjects will receive daily doses of CST-103 co-administered with CST-107 or matching placebo for 14 days. Each treatment period will be separated by a washout period of 14 days (+5-day window).
 
A comprehensive list of all study procedures is provided in the Schedule of Events.

------------------	---

[figure not shown]

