## 6. GENERAL DATA HANDLING CONVENTIONS

### 6.1. Reference Dates

- Screening date is defined as the eCRF provided date on which a subject was screened for trial entry.
- Treatment start date is defined as the date of first dose of study drug. Each treatment period will have a treatment start date (i.e., in order to determine AEs occurring during a treatment).
- Treatment end date is defined as the date of last dose of study drug.
- Safety data, such as AEs and laboratory assessments will use the treatment start date as a reference date.
- Study day will be based on treatment start date as a reference date.

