### 6.3. Baseline and Post-Baseline Changes

Unless stated otherwise, baseline and post-baseline change values will be based on the following:

- Baseline will be based on the last non-missing value collected prior to or on the treatment start date and time. Post-baseline values will be those collected after the treatment start date and time.
- Change from baseline is defined as: value – baseline value.

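### The C-SSRS tables stated in SAP 10.6 do not separate passive ideation allowed at entry from new intent or plan, and they mislabel the baseline (minor)

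*SAP*

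**What the plan says.** SAP 10.6 defines three 0/1 indicators: ideation (items 1 to 5), behavior (items 6 to 10), and either. It then states four tabulations. The first is general: "The number and percentage of subjects with any suicidal ideation and/or suicidal behavior following the first dose of study drug will be tabulated". The other three count subjects positive on each indicator; the ideation one counts those "who experience any one of the five suicidal ideation events at least once during treatment through follow-up will be tabulated".

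The section also says "The outcome of the C-SSRS is a numerical score obtained from the 10 categories stated above", without giving a scoring rule or a table for that score. It refers to a published scoring and analysis guide for method, and adds: "Results from the C-SSRS will be presented in a listing".

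On timing, 10.6 says "The C-SSRS will be completed at Day 1 (Baseline), Day 7, Day 14, and Follow-Up". The schedules disagree for Period 1. Protocol Schedule of Events footnote 25, and SAP Appendix 2 footnotes 24 (AUS/NZ) and 23 (UK/Belgium), all say there is no C-SSRS on Day 1 of Treatment Period 1. A Screening assessment does exist; the Protocol Synopsis (Study Procedures) lists "ECGs, Columbia-Suicide Severity Rating Scale (C-SSRS), safety laboratory tests" among the screening tests. The SAP 6.3 default baseline is the "last non-missing value collected prior to or on the treatment start date and time", and SAP 6.1 adds: "Each treatment period will have a treatment start date".

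SAP 10 presents safety summaries other than laboratory data by the treatment the subject was on when the data were collected. SAP 10.1 assigns washout adverse events to the Period 1 treatment, and later events up to the end of study to the Period 2 treatment. SAP 10.6 has no such rule.

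**The concern.** Protocol 1.3 names suicidal ideation as a concern for centrally acting drugs, and Protocol 2.1 describes Cohort A as having depressive symptoms. Exclusion 15 draws its line at items 4 and 5 (intent or plan). No table stated in 10.6 shows who crosses that line on treatment, and none uses a pre-dose value. Elsewhere the SAP does show grade and change: QTcF bands for level and for change (10.4), laboratory shift tables (10.2), and TEAEs by maximum severity (10.1).

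What is at stake is a misleadingly even row. Stable passive ideation on one treatment and new intent or plan on the other can give the same entry. Separately, two programmers working from 10.6 could place the Period 2 Day 1 assessment under different treatments.

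**Working it through.** The documents give no C-SSRS rate, so there is no plan figure to reproduce. The check is on how the tables are defined.

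**Does any stated table use a pre-dose value or isolate items 4 and 5?** Of the four tabulations, 0 use a pre-dose value and 0 isolate items 4 and 5.

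**What the indicator distinguishes.** Five Yes/No items give 2^5 = 32 patterns, of which 31 set the indicator to 1. Of those, 2^3 - 1 = 7 involve items 1 to 3 only and 31 - 7 = 24 include item 4 or 5. All 31 give the same entry.

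**Which escalations it can show.** Take the highest ideation category as 0 to 5. Eligible Screening levels are 0 to 3. These are counts of possible moves, not probabilities.
- Upward moves: 5 + 4 + 3 + 2 = 14.
- From level 0, where the indicator switches on: 5.
- From levels 1 to 3, where it stays at 1: 4 + 3 + 2 = 9. Six of these (3 starting levels x 2) reach item 4 or 5. The other three (1 to 2, 1 to 3, 2 to 3) would show only in a worsening row.

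**Effect on the comparison by treatment (assumed values).** Let n = 40 (the planned total, SAP 4.3), all taking both treatments. Two subjects reach items 4 or 5 on active only; m of those two also have ideation on placebo; k others have ideation on both.
- Active row = (k + 2)/n; placebo row = (k + m)/n; difference = (2 - m)/n, whatever k is.
- With k = 4: m = 0 gives 6/40 v 4/40 (15% v 10%); m = 1 gives 6/40 v 5/40 (15% v 12.5%); m = 2 gives 6/40 v 6/40 (15% v 15%).
- Planned differences: 5.0, 2.5 and 0 points. The item 4 or 5 row is 2/40 v 0/40 (5% v 0%) in every case.
- In an assumed 20-subject disease-type row, the planned differences are 10, 5 and 0 points.

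**Baseline.** For Period 1, SAP 6.3 resolves to Screening, because no Day 1 value exists. For Period 2, SAP 6.1 and 6.3 together point to Day 1, provided the assessment precedes dosing. Neither document says that it does. In Protocol 5.1.1.3 the FERT entry is marked as pre-dose; the C-SSRS entry has no timing.

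**Attribution.** A completer has six C-SSRS assessments after first dose: Period 1 Days 7 and 14; Period 2 Days 1, 7 and 14; and Follow-Up. With Follow-Up under Period 2, the split between periods is:
- Period 2 Day 1 counted under Period 1: 3 v 3.
- Counted under Period 2: 2 v 4.
- Treated as a baseline and not counted: 2 v 3.

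The wording of 10.6 does not settle which applies.

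**The case against.** The strongest reply has five parts.

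- **The guide.** 10.6 says the C-SSRS will be evaluated by the methods of a cited guide, which may include graded or baseline-referenced tables. This stands as a limit. A reader might infer that the analysis as a whole lacks grade and change; the documents support that only for the tables 10.6 states.
- **The score.** 10.6 calls a numerical score the outcome, and the SAP 5 defaults could summarise it. That is possible, but with no scoring rule or table given, the score cannot be relied on to show items 4 and 5.
- **The crossover.** A reader might infer that the missing baseline biases the treatment comparison. It does not follow: subjects with ideation on both treatments add k to both rows and cancel. What remains is masked escalation, and complete masking needs m = 2, a constructed case.
- **Other routes.** A reader might infer that escalation would go unseen. The by-subject listing would show it, behavior has its own row, and a worsening reported as an adverse event reaches the TEAE tables. Protocol 8.10 planned only a listing, so the SAP already goes further. All of this stands, though a listing gives no summary by treatment.
- **The label.** A reader might also infer that no baseline exists. One does: Screening, under the SAP 6.3 default. The Day 1 label is largely a wording error. However, Period 2 Day 1 still meets the rule of counting after first dose, and 10.6 has no counterpart to the adverse event washout rule.

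**Conclusion.** The point holds, and it is minor. The tabulations stated in SAP 10.6 do not separate passive ideation present at entry from new intent or plan, name a baseline visit that Period 1 lacks, and can count the Period 2 Day 1 baseline as an on-treatment event. The effect is confined to the C-SSRS tables of a descriptive study. Escalation is hidden in the comparison by treatment only when the escalating subjects also have ideation on the other treatment. The documents give no prevalence of ideation at entry, so the 0 to 5 point range at n = 40 illustrates the mechanism and is not a forecast. The conclusion is limited to what 10.6 states, because the content of the scoring guide is unknown here.

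**What to change.** In SAP 10.6, keep the planned indicators and make four changes:

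1. Add a row, by treatment, for subjects with any item 4 or 5 after dosing.
2. Add a row for subjects whose highest ideation category exceeds the pre-dose category, using Screening for Period 1 and pre-dose Day 1 for Period 2. Optionally repeat it with Screening as the reference for both periods, because the Period 2 value follows Period 1 exposure.
3. Replace the Day 1 baseline label with these two references, and state that the Period 2 Day 1 C-SSRS is done before dosing.
4. Attribute the Period 2 Day 1 assessment to the Period 1 treatment, and Follow-Up to the last treatment received (Period 2 for completers), matching the SAP 10.1 rule for adverse events.

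The cost is a few lines of SAP text and two sparse rows, with no new assessments. The Period 1 reference (Screening, Day -28 to Day -8) will be older than the Period 2 reference.
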